## Appendix 5. Drugs of interest

Groups	ATC code
Use of other respiratory drugs	
Mucolytics	R05CB, R05CB01, R05CB02, R05CB03, R05CB04, R05CB05, R05CB06, R05CB10, R05CB11, R05CB91, R05CB92
Theophylline	R03DA04, R03DA54, R03DA74, R03DB04
SABA	R03AC02, R03AC03, R03AC04, R03AC06
SAMA	R03BB01
SABA/SAMA	R03AL01, R03AL02
Drugs for COPD exacerbation treatment	
Oral corticosteroid	H02AB01, H02AB02, H02AB04, H02AB05, H02AB06, H02AB08, H02AB10, H02BX, H02BX91
Antibiotic for COPD exacerbation	J01AA02, J01CA04, J01CR02, J01CR05, J01EE01, J01DC01, J01DC02, J01DC03, J01DC04, J01DC05, J01DC06, J01DC07, J01DC09, J01DC14, J01DD01, J01DD02, J01DD04, J01DD05, J01DD06, J01DD07, J01DD08, J01DD12, J01DD13, J01DD14, J01DD52, J01DD62, J01DE01, J01DE02, J01FA01, J01EA02, J01EA03, J01EA06, J01EA07, J01EA08, J01FA09, J01FA10, J01FA15, J01FA91, J01MA01, J01MA02, J01MA03, J01MA04, J01MA06, J01MA07, J01MA09, J01MA12, J01MA14, J01MA15
Drugs for Medication history	

 
● Cardiovascular drugs
 
	
Anti-hypertensives	C02AA01, C02AA02, C02AA04, C02AB01, C02AB02, C02AC01, C02CA01, C02CA04, C02CA, C02CC02, C02DA01, C02DB02, C02DC01, C02DD01, C02LA01, C02LA50, C02LA51, C02LB01, C02LG02, C02N, C03AA01, C03AA03, C03AA06, C03AA07, C03AA, C03BA04, C03BA08, C03BA11, C03CA01, C03CA02, C03CA04, C03CC01, C03DA01, C03DA04, C03DB01, C03DB02, C03EA01, C03EA, C07AA01, C07AA02, C07AA03, C07AA05, C07AA06, C07AA07, C07AA12, C07AA15, C07AA19, C07AB02, C07AB03, C07AB04, C07AB05, C07AB07, C07AB09, C07AB12,

	C07AG01, C07AG02, C07BA68, C07BB02, C07CA03, C07CB03, C07DA06, C08CA01, C08CA02, C08CA03, C08CA04, C08CA05, C08CA07, C08CA08, C08CA09, C08CA12, C08CA13, C08CA15, C08DA01, C08DB01, C09AA01, C09AA02, C09AA03, C09AA04, C09AA05, C09AA06, C09AA07, C09AA08, C09AA09, C09AA16, C09BA01, C09BA02, C09BA04, C09BB04, C09BB05, C09BB, C09BB, C09CA01, C09CA02, C09CA03, C09CA04, C09CA06, C09CA07, C09CA08, C09CA09, C09DA01, C09DA03, C09DA04, C09DA06, C09DA07, C09DA08, C09DA09, C09DB01, C09DB02, C09DB04, C09DB07, C09DX01, C09DX03, C09DX04, C09XA02, C09XA52, C09XA53, C09XA54
Antiarrhythmics	C01AA04, C01AA05, C01AA07, C01AA08, C01AB01, C01AC01, C01BA01, C01BA02, C01BA03, C01BA04, C01BA08, C01BB01, C01BB02, C01BC03, C01BC04, C01BD01, C01BD07, C01CA02, C01CA04, C01CA06, C01EB10, C01EB17, C07AA01, C07AA02, C07AA03, C07AA05, C07AA07, C07AA12, C07AA15, C07AA19, C07AB02, C07AB03, C07AB04, C07AB05, C07AB07, C07AB09, C07AB12, C08DA01, C08DB01
Heart failure medications	C01AA04, C01AA05, C01AA07, C01AA08, C01AB01, C01AC01, C01CA02, C01CA07, C01CE02, C01EB09, C01EB17, C03CA02, C03CA04, C03DA04, C07AG02, C09AA01, C09AA02, C09AA03, C09AA04, C09AA05, C09AA06, C09AA07, C09AA08, C09AA09, C09AA16, C09CA01, C09CA02, C09CA03, C09CA04, C09CA06, C09CA07, C09CA08, C09CA09
Nitrates	C01DA02, C01DA05, C01DA08, C01DA14
● Lipid-lowering medications	
Lipid Modifying Agents, Plain	C10AA01, C10AA02, C10AA03, C10AA04, C10AA05, C10AA07, C10AA08, C10AB01, C10AB02, C10AB03, C10AB04, C10AB05, C10AB06, C10AB09, C10AC01, C10AC02, C10AC03, C10AD01, C10AD02, C10AD03, C10AD06, C10AD, C10AX02, C10AX09, C10AX13, C10AX14, C10AX

Proprietary confidential information © 2022 Boehringer Ingelheim International GmbH or one or more of its affiliated companies

Lipid Modifying Agents, Combinations	C10BA01, C10BA02, C10BA03, C10BA05, C10BX03
● Blood glucose-lowering medications	
Insulins and analogues	A10AB01, A10AB03, A10AB04, A10AB05, A10AB06, A10AB30, A10AC01, A10AC03, A10AC30, A10AD01, A10AD03, A10AD04, A10AD05, A10AD06, A10AE01, A10AE04, A10AE05, A10AE06, A10AE54
Blood glucose lowering drugs, excl. insulins	A10BA02, A10BA03, A10BB01, A10BB02, A10BB03, A10BB04, A10BB05, A10BB07, A10BB08, A10BB09, A10BB12, A10BB31, A10BD02, A10BD03, A10BD05, A10BD07, A10BD08, A10BD09, A10BD10, A10BD11, A10BD13, A10BD14, A10BD, A10BD15, A10BD19, A10BD20, A10BD21, A10BD24, A10BF01, A10BF02, A10BG02, A10BG03, A10BH01, A10BH02, A10BH03, A10BH04, A10BH05, A10BJ01, A10BJ02, A10BJ03, A10BJ05, A10BJ06, A10BK01, A10BK02, A10BK03, A10BK04, A10BX01, A10BX02, A10BX03, A10BX08
● Anticoagulants and antiplatelet agents	
Vitamin K antagonists	B01AA02, B01AA03
Heparin group	B01AB01, B01AB04, B01AB05, B01AB06, B01AB10
Platelet aggregation inhibitors excl. heparin	B01AC04, B01AC05, B01AC06, B01AC07, B01AC09, B01AC11, B01AC13, B01AC16, B01AC17, B01AC21, B01AC22, B01AC23, B01AC24, B01AC27, B01AC30
Enzymes	B01AD01, B01AD02, B01AD04, B01AD10, B01AD11
Direct thrombin inhibitors	B01AE07
Direct factor Xa inhibitors	B01AF01, B01AF02, B01AF03
Other antithrombotic agents	B01AX05
● Antibiotic	

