### **7.2 OUTCOMES**

#### **7.2.1 Primary outcomes**

##### **➤ Time to the first moderate or severe COPD exacerbations after index date**

The definition of moderate or severe COPD exacerbation:

- a. Moderate exacerbations will be defined as an outpatient visit with a diagnosis code for COPD in any field + a prescription for an oral corticosteroid or an antibiotic for respiratory infections
- b. Severe exacerbations will be defined as a hospitalization or emergency room visit with a primary diagnosis for COPD

Detailed diagnosis codes are listed in Annex.

Tio/Olo users will be matched to the comparator through 1:1 propensity score matching. For the analysis of the primary outcome, individuals will be followed up from the index date until the first moderate or severe COPD exacerbation. For detailed, please refer to section [10.1](#). As time-to-event data, the main analysis will be univariate proportional hazard regression analysis to estimate the hazard ratio (Tio/Olo vs. comparator) and its 95% confidence interval (CI). Detailed analytic approach is described in Section [10.1](#).

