# BOEHRINGER INGELHEIM Group of Companies

## Statistical and Epidemiological Analysis Plan (SEAP) for Non-Interventional Studies (NIS)

c40729787-01

Page 35 of 38

Proprietary confidential information © 2022 Boehringer Ingelheim International GmbH or one or more of its affiliated companies

Antibacterials for systemic use	J01AA01, J01AA02, J01AA03, J01AA04, J01AA06, J01AA07, J01AA08, J01AA09, J01AA12, J01AA56, J01BA01, J01BA02, J01BA51, J01CA01, J01CA02, J01CA03, J01CA04, J01CA06, J01CA08, J01CA09, J01CA10, J01CA12, J01CA13, J01CA14, J01CA15, J01CA16, J01CA18, J01CA20, J01CA91, J01CE01, J01CE02, J01CE08, J01CE09, J01CE30, J01CF01, J01CF02, J01CF04, J01CF05, J01CG01, J01CR01, J01CR02, J01CR03, J01CR04, J01CR05, J01CR50, J01CR50, J01CR50, J01DB01, J01DB02, J01DB03, J01DB04, J01DB05, J01DB06, J01DB07, J01DB08, J01DB09, J01DC01, J01DC02, J01DC03, J01DC04, J01DC05, J01DC06, J01DC07, J01DC09, J01DC14, J01DD01, J01DD02, J01DD04, J01DD05, J01DD06, J01DD07, J01DD08, J01DD12, J01DD13, J01DD14, J01DD52, J01DD62, J01DE01, J01DE02, J01DF01, J01DH02, J01DH03, J01DH04, J01DH51, J01DI02, J01DI54, J01E, J01EA01, J01EB01, J01EB02, J01EB05, J01EB06, J01EB20, J01EC, J01EC01, J01EC02, J01EC20, J01ED01, J01ED05, J01ED20, J01EE01, J01FA01, J01EA02, J01EA03, J01EA06, J01EA07, J01EA08, J01FA09, J01FA10, J01FA15, J01FA91, J01FF01, J01FF02, J01GA01, J01GB01, J01GB03, J01GB04, J01GB05, J01GB06, J01GB07, J01GB08, J01GB09, J01GB11, J01MA01, J01MA02, J01MA03, J01MA04, J01MA06, J01MA07, J01MA09, J01MA12, J01MA14, J01MA15, J01MB01, J01MB02, J01MB03, J01MB04, J01MB08, J01RA02, J01XA01, J01XA02, J01XB, J01XB01, J01XC01, J01XD01, J01XD02, J01XD03, J01XE, J01XE01, J01XE02, J01XX01, J01XX04, J01XX05, J01XX07, J01XX08, J01XX09, J01XX91
Antimycotics for systemic use	J02AA01, J02AB01, J02AB02, J02AC01, J02AC02, J02AC03, J02AC04, J02AC05, J02AX01, J02AX04, J02AX05, J02AX06
Antimycobacterials	J04AA03, J04AB01, J04AB02, J04AB03, J04AB04, J04AB91, J04AC01, J04AC51, J04AD01, J04AK01, J04AK02, J04AK04, J04AM02, J04AM03, J04AM05, J04AM06, J04AM07, J04BA01, J04BA02

● Antineoplastic agents	
Alkylating agents	L01AA01, L01AA02, L01AA03, L01AA06, L01AA09, L01AB01, L01AC01, L01AC03, L01AD01, L01AD02, L01AD06, L01AX03, L01AX04
Antimetabolites	L01BA01, L01BA04, L01BA05, L01BB02, L01BB03, L01BB04, L01BB05, L01BB06, L01BC01, L01BC02, L01BC03, L01BC05, L01BC06, L01BC07, L01BC53, L01BC59
Plant alkaloids and other natural products	L01CA01, L01CA02, L01CA04, L01CB01, L01CD01, L01CD02, L01CE01, L01CE02

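### Five codes in the SAP's antibiotic lists very probably carry the wrong prefix (J01EA for J01FA), so some moderate exacerbations treated only with those agents would be missed or dated late

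*SAP*

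**What the plan says.** SAP section 7.2.1 defines a moderate exacerbation as an outpatient visit with a COPD diagnosis code plus "a prescription for an oral corticosteroid or an antibiotic for respiratory infections". A severe exacerbation needs no drug code: "Severe exacerbations will be defined as a hospitalization or emergency room visit with a primary diagnosis for COPD".

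Appendix 5 of the SAP supplies the drug codes. Under drugs for exacerbation treatment, the antibiotic row contains "J01FA01, J01EA02, J01EA03, J01EA06, J01EA07, J01EA08, J01FA09, J01FA10, J01FA15, J01FA91".

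Further down Appendix 5, the row of systemic antibacterials used for medication history repeats the same five codes in the same position: "J01EE01, J01FA01, J01EA02, J01EA03, J01EA06, J01EA07, J01EA08, J01FA09, J01FA10, J01FA15, J01FA91, J01FF01". Earlier in that same row, the J01E block opens with "J01E, J01EA01, J01EB01, J01EB02".

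**The concern.** An ordered list of J01FA codes switches prefix for five consecutive entries and then switches back, with no break in the suffixes. If the prefix is wrong, J01FA02, J01FA03, J01FA06, J01FA07 and J01FA08 are absent from the rule that finds antibiotic-treated exacerbations, and five codes nobody meant to include take their place.

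The exacerbation row supports several parts of the analysis:

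- the moderate component of the primary outcome (SAP 7.2.1);
- the annualized rate of moderate or severe exacerbations (SAP 7.2.2);
- the exacerbation history in the 12 months and the 30 days before entry (SAP 7.3);
- probably the second-course-of-antibiotics criterion for severe COPD (SAP 7.3), although the SAP does not say which list that criterion uses.

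The systemic-antibacterial row supplies the baseline antibiotic covariate. SAP section 10.1 puts every covariate except season into the propensity score and performs the matching once only. A code error found after matching would therefore be awkward to repair.

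**Working it through.** The plan states no figure on this point, so there is none to reproduce. The check compares the two lists with their own ordering.

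**1. Exacerbation-antibiotic row (48 codes).**
- Suffixes from J01FA01 to J01FA91, in printed order: 01, 02, 03, 06, 07, 08, 09, 10, 15, 91. They ascend throughout.
- Prefixes over the same ten entries: J01FA once, J01EA five times, J01FA four times.
- Affected share: 5/48 = 10% of the row and 5/10 of the run.
- Places where a code is followed by a lower one: two (J01EE01 to J01DC01, and J01FA01 to J01EA02).
- After changing the five prefixes to J01FA: one such place remains (J01EE01 to J01DC01), and there are no duplicates.

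**2. Systemic-antibacterial row (157 entries).**
- Places where a code is followed by a lower one: exactly one, J01FA01 to J01EA02.
- After changing the five prefixes: none. No new duplicate appears (J01CR50 is printed three times before and after the change).
- J01EA01 stands between J01E and J01EB01. J01EA02 to J01EA08 would have followed it there if they had been meant.

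**3. Are the J01FA versions present elsewhere?** None of J01FA02, J01FA03, J01FA06, J01FA07 or J01FA08 appears in either row, so nothing else in the lists makes up for the change.

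**4. Could it be a text-extraction fault?** The same five codes differ in two separate tables, while the J01FA codes on either side are read correctly in both. One source error copied into both tables fits better than two identical misreadings.

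**5. What the rule does if programmed as printed.**

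| Treatment at an outpatient COPD visit | Counted as moderate? |
|---|---|
| Oral corticosteroid, with or without one of the five agents | Yes |
| One of the five agents plus another listed antibiotic | Yes |
| One of the five agents only | No |

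In the last case the patient stays at risk. If a later qualifying event falls within on-treatment follow-up, the first event is dated late. If none does, the patient is censored without an event. Severe events need only a hospitalization or emergency visit with a primary COPD diagnosis, so they are unchanged.

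**The case against.** **The ordering evidence is weaker where it matters most.** The exacerbation row is not fully sorted, since J01EE01 precedes J01DC01. For the list that defines the outcome, the inference rests on the suffix sequence and on agreement with the systemic row. That stands as a limit. But one stray code does not explain five consecutive misplaced codes whose suffixes fit the gap, and the systemic row has no other break in 157 entries.

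**The intended codes need outside confirmation.** The lists give no drug names for individual codes. Whether the five J01FA codes were intended, and occur in the NHI data, must be checked against the drug file. This stands, and the correction should follow the check.

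**A reader might infer that all exacerbations treated with these agents are lost.** The definition does not support that. A corticosteroid or another listed antibiotic still makes the visit count, and a later event can still be recorded.

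**A reader might also try to put a number on the loss.** HR 0.9, 90% power and two-sided alpha 0.05 imply 4 × (1.96 + 1.2816)² / (ln 0.9)² ≈ 3,786 events. Suppose 30–70% of moderate events are antibiotic-only and 5–20% of those courses use the five agents. The product is 1.5–14%, or about 57–530 events. This fails for three reasons:

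- both shares are assumptions, and the documents give no prescribing frequencies;
- a share of moderate events is applied to a total that includes severe ones;
- delayed events are counted as lost.

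Even the extreme case, with 3,786 − 530 = 3,256 events left, gives power Φ(0.10536 × √3,256 / 2 − 1.96) ≈ 85% instead of 90%.

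**A biased hazard ratio is also tempting to infer.** If under-capture is similar in the two arms, both hazards shrink by about the same factor and the ratio largely holds. Bias requires use of these agents to differ by arm, and the documents give no evidence either way.

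**Conclusion.** The point holds as a very probable copied prefix error in both Appendix 5 lists. It affects 5 of the 48 codes in the row that defines antibiotic treatment of an exacerbation. As printed, the primary outcome would leave out visits treated only with the intended agents, so some first events would be missed or dated late. The annualized rate, the exacerbation history, the baseline antibiotic covariate and hence the propensity score are exposed to the same error. Severe events are not.

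The conclusion assumes that the Appendix 5 exacerbation row is the list used for the respiratory antibiotics in section 7.2.1. It is the only antibiotic row labelled for that purpose. It also assumes that the lists are programmed literally. The documents do not allow a count of affected events, or a size or direction for any bias in the hazard ratio.

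**What to change.** Before the outcome and the propensity score are programmed:

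1. Check J01EA02, J01EA03, J01EA06, J01EA07 and J01EA08, and their J01FA counterparts, against the ATC index and the NHI drug file.
2. Once confirmed, change the prefix to J01FA for these five codes in both Appendix 5 rows. Leave J01EA01 in the systemic row as it is.

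The cost is a code-list edit and a short look-up. Because matching is done once, the edit should come before matching.

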# BOEHRINGER INGELHEIM Group of Companies

## Statistical and Epidemiological Analysis Plan (SEAP) for Non-Interventional Studies (NIS)

c40729787-01

Page 35 of 38

Proprietary confidential information © 2022 Boehringer Ingelheim International GmbH or one or more of its affiliated companies

Antibacterials for systemic use	J01AA01, J01AA02, J01AA03, J01AA04, J01AA06, J01AA07, J01AA08, J01AA09, J01AA12, J01AA56, J01BA01, J01BA02, J01BA51, J01CA01, J01CA02, J01CA03, J01CA04, J01CA06, J01CA08, J01CA09, J01CA10, J01CA12, J01CA13, J01CA14, J01CA15, J01CA16, J01CA18, J01CA20, J01CA91, J01CE01, J01CE02, J01CE08, J01CE09, J01CE30, J01CF01, J01CF02, J01CF04, J01CF05, J01CG01, J01CR01, J01CR02, J01CR03, J01CR04, J01CR05, J01CR50, J01CR50, J01CR50, J01DB01, J01DB02, J01DB03, J01DB04, J01DB05, J01DB06, J01DB07, J01DB08, J01DB09, J01DC01, J01DC02, J01DC03, J01DC04, J01DC05, J01DC06, J01DC07, J01DC09, J01DC14, J01DD01, J01DD02, J01DD04, J01DD05, J01DD06, J01DD07, J01DD08, J01DD12, J01DD13, J01DD14, J01DD52, J01DD62, J01DE01, J01DE02, J01DF01, J01DH02, J01DH03, J01DH04, J01DH51, J01DI02, J01DI54, J01E, J01EA01, J01EB01, J01EB02, J01EB05, J01EB06, J01EB20, J01EC, J01EC01, J01EC02, J01EC20, J01ED01, J01ED05, J01ED20, J01EE01, J01FA01, J01EA02, J01EA03, J01EA06, J01EA07, J01EA08, J01FA09, J01FA10, J01FA15, J01FA91, J01FF01, J01FF02, J01GA01, J01GB01, J01GB03, J01GB04, J01GB05, J01GB06, J01GB07, J01GB08, J01GB09, J01GB11, J01MA01, J01MA02, J01MA03, J01MA04, J01MA06, J01MA07, J01MA09, J01MA12, J01MA14, J01MA15, J01MB01, J01MB02, J01MB03, J01MB04, J01MB08, J01RA02, J01XA01, J01XA02, J01XB, J01XB01, J01XC01, J01XD01, J01XD02, J01XD03, J01XE, J01XE01, J01XE02, J01XX01, J01XX04, J01XX05, J01XX07, J01XX08, J01XX09, J01XX91
Antimycotics for systemic use	J02AA01, J02AB01, J02AB02, J02AC01, J02AC02, J02AC03, J02AC04, J02AC05, J02AX01, J02AX04, J02AX05, J02AX06
Antimycobacterials	J04AA03, J04AB01, J04AB02, J04AB03, J04AB04, J04AB91, J04AC01, J04AC51, J04AD01, J04AK01, J04AK02, J04AK04, J04AM02, J04AM03, J04AM05, J04AM06, J04AM07, J04BA01, J04BA02

● Antineoplastic agents	
Alkylating agents	L01AA01, L01AA02, L01AA03, L01AA06, L01AA09, L01AB01, L01AC01, L01AC03, L01AD01, L01AD02, L01AD06, L01AX03, L01AX04
Antimetabolites	L01BA01, L01BA04, L01BA05, L01BB02, L01BB03, L01BB04, L01BB05, L01BB06, L01BC01, L01BC02, L01BC03, L01BC05, L01BC06, L01BC07, L01BC53, L01BC59
Plant alkaloids and other natural products	L01CA01, L01CA02, L01CA04, L01CB01, L01CD01, L01CD02, L01CE01, L01CE02
Cytotoxic antibiotics and related substances	L01DA01, L01DB01, L01DB02, L01DB03, L01DB04, L01DB06, L01DB07, L01DC01, L01DC03, L01DC04
Protein kinase inhibitors	L01EA01, L01EA02, L01EA03, L01EA05, L01EB01, L01EB02, L01EB03, L01EB04, L01EB07, L01EC01, L01EC02, L01ED01, L01ED02, L01ED03, L01ED04, L01ED05, L01EE01, L01EF01, L01EF02, L01EG01, L01EG02, L01EH01, L01EJ01, L01EK01, L01EL01, L01EM02, L01EX01, L01EX02, L01EX03, L01EX04, L01EX05, L01EX07, L01EX08, L01EX09, L01EX10, L01EX14
Other antineoplastic agents	L01XA01, L01XA02, L01XA03, L01XB01, L01XC02, L01XC03, L01XC06, L01XC07, L01XC08, L01XC12, L01XC13, L01XC14, L01XC15, L01XC17, L01XC18, L01XC19, L01XC21, L01XC24, L01XC26, L01XC31, L01XC32, L01XF01, L01XG01, L01XG02, L01XG03, L01XK01, L01XK04, L01XX02, L01XX05, L01XX11, L01XX23, L01XX27, L01XX35, L01XX41, L01XX52, L01XX
Hormones and related agents	L02AA01, L02AA91, L02AB01, L02AB02, L02AE01, L02AE02, L02AE03, L02AE04
Hormone antagonists and related agents	L02BA01, L02BA02, L02BB01, L02BB03, L02BB04, L02BB05, L02BG01, L02BG03, L02BG04, L02BG06, L02BX02, L02BX03

**Appendix 6. Procedure codes for oxygen therapy or nebuliser therapy**

Description	Procedure codes
Oxygen therapy	47054C, 54007C1, 57001B, 57002B, 57003C, 57004C, 57019C, 57020C, 57023B, 57029C
Nebuliser therapy	57021C, 57022C, 57024B

